1.2. Schema

Figure 1 Study Schematic

1.3. Schedule of Activities (SoA)

The Schedule of Activities (SoA) for this study are provided in Table 1. Study visits will include:

- In-clinic visits (with a marker of "a" in Table 1)
- Telemedicine visits (with a marker of "b"), where permitted by local regulations
- Optional home nursing visits (with a marker of "c"), where permitted by local regulations

Refer to study reference manual (SRM) for further details.

Table 1 Schedule of Activities Table

	(Visit 1) ^{a, d}						Tr	eatn	nent	Peri	od						Withdraw	/Follow Up	-
Procedure									Wee	k							EW Visit	Follow-up	
Procedure	ing	0	4	8	12	16	20	24	26	28	32	36	40	44	48	52	26 or 52	30/56	Notes
	eeu							i i				7 da						•	
	Screening	2a	3a	4 c	5a	6 ^b	7a	8b	9a					14 ^b	15a	16a	a, e	b, e	
Eligibility Assessments																ı		L	
Informed Consent	х																		To be signed before any study procedures. Can occur at a separate visit, prior to Screening, if preferred.
Optional Genetic Informed Consent	Х																		Not applicable for China. Informed consent for optional genetics sample must be obtained before collecting a sample.
Optional Biomarker Informed Consent	Х																		Not applicable for China. Informed consent for optional exploratory biomarkers must be obtained before collecting a sample.
Inclusion and exclusion criteria	Χ																		·
Demography	Χ																		
Medical history; Past and current medical conditions	х																		Medical history includes past and current medical conditions for the preceding 12 months including cardiovascular medical history as well as family history of premature cardiovascular disease, CRSwNP disease, CRSwNP/eosinophilic chronic rhinosinusitis (ECRS) and

	(Visit 1)a, d						Tr	eatn	nent	Peri	od						Withdraw	/Follow Up	
Procedure	S								Weel									Follow-up	Notes
. 100044.0	Screening	0	4	8	12	16	20	24	26			36		44	48	52	26 or 52	30/56	Notes
	ee e											7 da							
	Sci	2a	3a	4 c	5a	6 ^b	7a	8 ^b	9a	10a	11a	12 ^b	13a	14 ^b	15a	16a	a, e	b, e	
																			asthma therapy, substance usage, smoking history, asthma and exacerbation history, and concomitant medications for the preceding 12 months.
History of NP surgery	Χ																		
History of systemic CS use including for CRSwNP	Χ																		
Randomization & Study Intervention																			
Review of randomization criteria		Χ																	
Randomization		Χ																	Randomization Day is Day 1.
Study Intervention Administration		Χ							Χ										A minimum of 2 hours observation post-injection (at randomization and at Week 26; V9).
Device deficiencies review		Χ							Χ										
Safety Assessments																			
Physical exam	Х	X							Χ							X	Х		Height to be measured at Screening (V1) only. Weight does not need to be collected at V9. At V2 and V9, physical examination to be performed prior to dosing.
Vital signs	Х	Χ		х			Х		Х	Х			Х		Χ	Х	Х		Temperature, systolic and diastolic blood pressure and heart rate.
12-lead ECG	Х	Χ	Χ						X	Χ						Х	Х		ECG must be performed and assessed pre-dose. Twelve-lead ECG central over-read

	Screening (Visit 1)a, d						Tı	reatn	nent	Peri	od						Withdraw	/Follow Up	Natas
Procedure	į.							1	Wee	k								Follow-up	
	l in	0	4	8	12	16	20	24	26					44	48	52	26 or 52	30/56	Notes
	ee e											-7 da							
	Sci	2a	3a	4 c	5a	6 ^b	7a	8 b	9a	10a	11a	12b	13a	14b	15a	16a	a, e	b, e	
																			values should be used at all visits with the exception of V2 and V9 where 12-lead ECG machine read values should be used.
SAE review	х	Х	Х	х	Х	Х	Х	Х	Х	Х	X	Х	Х	Х	Х	Х	х	х	Any SAEs assessed as related to study procedures or related to a GSK product will be recorded from the time a participant consents to participate in the study.
AE review		Х	Χ	Χ	Χ	Χ	Χ	Χ	Χ	Χ	Χ	Χ	Χ	Χ	Χ	Χ	Х	Х	,
Concomitant medication review (including INCS)		Χ	Χ	Х	Χ	Χ	Χ	Χ	Χ	Χ	Χ	Χ	Χ	Χ	Χ	Χ	Х	Х	
Efficacy Assessment																			
Assessment of endoscopic NP score	X	х			х		X		х		X		х		X	х	Х		For V2, the nasal endoscopy assessment may be performed up to 7 days prior to the clinic visit. Nasal endoscopy must occur prior to randomization. For all other visits the nasal endoscopy assessment must not exceed the protocol defined windows of ±7 days from the nominal study visit.
CT Scan	Х															Х	X		CT scan is mandatory unless not approved by local ethics committee or institutional review board. The first CT

	(Visit 1)a, d						Tı	reatn	nent	Peri	od						Withdraw	/Follow Up	
Procedure	Ξ		Week EW Visit Follow												Follow-up	No.4			
1 1000dail0	Screening	0	4	8	12	16	20	24	26	28				44	48	52	26 or 52	30/56	Notes
	ree				_						sit (±			1	1			1 .	
	Ŏ	2a	3ª	40	5a	6b	7a	86	ga .	1U ^a		120	13ª	140	15ª	10a	a, e	b, e	scan must be performed prior to randomization and should be the last assessment performed, where possible. If the first CT scan cannot be performed as the last assessment before randomization, the subject should have completed their screening visit and all screening lab results, the central NP score and ECG central over-read results should be assessed by the PI before a CT scan is conducted. The second CT scan should be performed at V16 or EW visit (up to 14 days prior to the nominal study visit). Note: If a participant is permanently discontinued both from the study intervention and from the study, and the second dose of study intervention was not received, decision on performing CT scan during EW visit at Week 26 will be made by the investigator in consultation with the Medical

	(Visit 1)a, d						Tr	eatn	nent	Peri	od						Withdraw	/Follow Up	
Procedure	Ξ							1	Weel	k							EW Visit	Follow-up	Notes -
1 Toocdard	Screening	0	4	8	12	16	20	24	26	28	32	36	40	44	48	52	26 or 52	30/56	Notes
	eel									Vi	sit (±	-7 da	iys)						
	Sci	2a	3a	4 c	5a	6 ^b	7a	8 b	9a	10a	11a	12 ^b	13a	14b	15ª	16a	a, e	b, e	
																			Monitor. Please refer to Pregnancy test (WOCBP only).
Assessment of Actual NP Surgery or planned NP Surgery		Х	Х	Х	Х	Х	X	X	X	Х	X	X	X	Х	X	Х	Х		Wherever possible (and when optional consent provided for exploratory biomarkers), the removed tissue from a nasal surgery will be collected and stored. Not applicable for China.
Assessment of systemic CS and antibiotics dose and duration including for CRSwNP		Χ	Χ	Х	Х	Χ	Χ	Χ	Χ	Χ	Χ	Χ	Χ	Χ	Χ	Χ	Х	Х	
Patient-Reported Outcomes																			
Dispensing and Training of the eDiary	Χ																		
eDiary Compliance Check		Χ	Χ	Χ	Χ	Χ	Χ	Χ	Χ	Χ	Χ	Χ	Χ	Χ	Χ	Χ	Х		
eDiary Collection																Χ	Х		
Individual symptom scores (including nasal obstruction, rhinorrhea [runny nose], loss of smell, facial pain, and mucus in throat) (VRS) ^f	Χ	Χ	X	Х	X	X	Χ	X	X	Χ	Χ	Χ	Χ	Χ	X	Χ	X		Performed using eDiary. eDiary will be completed by participants in the morning between Screening Visit (V1) and V16.
Overall symptoms score (VAS) ^f	X	Х	Χ	х	Х	Х	Χ	Χ	Χ	Х	Х	Χ	Χ	Х	Χ	Χ	X		Performed using eDiary. eDiary will be completed by participants in the morning between Screening Visit (V1) and V16.
Nasal obstruction score (VAS)f	Χ	Χ						Χ								Χ	Х		Performed using eDiary.
SNOT-22f		Χ	Χ	Χ	Χ	Χ	Χ	Χ	Χ	Χ	Χ	Χ	Χ	Χ	Χ	Χ	Х		Performed using eDiary.
PGISf		Χ	Χ	Х	Χ			Χ					Χ			Χ	Х		Performed using eDiary. The PGIS will ask the patient to

	(Visit 1)a, d						Tr	eatn	nent	Peri	od						Withdraw	/Follow Up	
Procedure	y (V								Wee									Follow-up	Notes
	Screening	0	4	8	12	16	20	24	26			36		44	48	52	26 or 52	30/56	Notes
	reel										_	7 da	, ,						
	Scı	2a	3a	4 c	5a	6 ^b	7a	8 b	9a	10a	11a	12 ^b	13a	14b	15a	16a	a, e	b, e	
																			rate the severity of their nasal polyps symptoms over the last 4 weeks.
PGICf			Х	х	Х			Х					Х			Х	Х		Performed using eDiary. The PGIC will ask the patient to rate the change in their nasal symptoms since the start of trial medication.
ACQ-5 ^f		Χ		Х		Х		Х	Χ		Χ		Χ		Х	Х	Х		For asthmatic participants only. Performed using eDiary.
Review for asthma exacerbations		X	X	x	X	X	X	X	X	x	X	X	X	Х	х	х	х	Х	For asthmatic participants only. An asthma exacerbation is defined as worsening of asthma requiring systemic corticosteroids (IV or oral steroid) for at least 3 days or a single IM CS dose and/or emergency department visit, or hospitalization.
SF-36 ^f		Χ		Χ					Χ				Χ			Χ	Х		Performed using eDiary.
WPAI-GH ^f		Χ		Х					Χ				Χ			X	Х		Performed using eDiary.
Laboratory Assessments														1			l		In
Parasitic screening	X																		Parasitic screening is only required in countries with high-risk or for participants who have visited high-risk countries in the past 6 months. Please refer to SRM for full list of high-risk countries. Sites should use local

TMF-19443864

	(Visit 1)a, d						Tr	eatm	nent	Peri	od						Withdraw	/Follow Up	
Procedure	g (Vi								Nee									Follow-up	Notes
1000000	Screening	0	4	8	12	16	20	24	26			36		44	48	52	26 or 52	30/56	Notes
	ree					1		· ·				7 da		1	1		ı		
	Sc	2a	3a	4 c	5a	6 ^b	7a	8 b	9a	10a	11a	12 ^b	13a	14b	15ª	16ª	a, e	b, e	
																			laboratories. If sites wish to use central laboratories, they should note that the central test is stool microscopy for ova and parasites. For details of the organisms detected by this test refer to the parasitic screening section of the SRM.
Clinical chemistry (including liver chemistry)	Χ	Χ	Χ	Χ	Χ		Χ		Χ	Χ			Χ			Χ	Х		
Urinalysish	X	X							X				X			X	Х		Urinalysis to be performed at local laboratories using dipstick test. If results are abnormal (blood or protein is abnormal [evidence of microalbuminuria or hematuria of ≥1+]) a second urine sample should be taken and sent to central laboratory.
Hematology	X	X	X	X	X		X		X	X	X		X		X	X	X		For hematology samples collected after Randomization, the absolute and differential (%) values of eosinophils, lymphocytes, basophils, neutrophils and monocytes will not be reported to site staff and Sponsor (to maintain the treatment blind). However, sites will be sent total white blood counts throughout the

	Screening (Visit 1) ^{a, d}						Tr	eatn	nent	Peri	iod						Withdraw	/Follow Up	
Procedure	9 (V								Wee									Follow-up	Notes
	nin	0	4	8	12	16	20	24	26			36		44	48	52	26 or 52	30/56	Notes
	ree							1				£7 da			1		1		
	Sc	2a	3a	4 c	5a	6 ^b	7a	8 b	9a	10a	11a	12b	13ª	14b	15ª	16ª	a, e	b, e	
																			study. Samples should be taken prior to dosing at V2 and V9.
Pregnancy test (WOCBP only)	X	x	х	X	х	X	х	X	X		х	х	X	х	X	X	X	X	For WOCBP, a serum pregnancy test should be done at Screening Visit, at V16, and EW Visit. Highly sensitive urine pregnancy tests should be done for all other time points. Urine pregnancy test should also be performed within 24 hours prior to any CT scan and results assessed prior to the CT scan. If a urine test cannot be confirmed as negative (e.g., an ambiguous result), a serum pregnancy test is required. Participants who withdraw early from the study should have a urine pregnancy test 4 weeks after the EW Visit.
PK samples		Х	Х	Х	Х		х		Х	Х	Х		Х			Х	Х		Must be performed pre-dose at V2 and V9. PK samples at Week 52 (Visit 16/EW Visit) will be collected for approximately 200 participants; sites will be notified once 200 samples

	isit 1)ª, d						Tı	reatn	nent	Peri	od						Withdraw	/Follow Up	
Procedure	Screening (Visit								Wee									Follow-up	Notes
. 10004410	nin	0	4	8	12	16	20	24	26					44	48	52	26 or 52	30/56	Notes
	reel				,		,		,			7 da						_	
	Sc	2a	3a	4 c	5a	6 ^b	7a	8b	9a	10a	11a	12 ^b	13a	14b	15a	16a	a, e	b, e	
																			have been collected.
IL-5 samples		Х	Χ		Х				Х				Χ			Χ	Х		Must be performed pre-dose at V2 and V9.
Complement C3 and C4 sample		Χ			Χ				Χ				Χ			Χ	Χ		
Total IgE sample		Χ																	
Anti-MPO antibody, anti-PR3 antibody, ANA including anti-dsDNA Ab		X																	Collected baseline (pre-dose) serum sample will be stored and may be tested for ANCA, (anti-MPO antibody, anti-PR3 antibody) and ANA including anti-dsDNA Ab, if necessary (Section 8.6.3)
Immunogenicity		Χ	Χ	Х	Χ				Х				Χ			Χ	Х		Must be performed pre-dose at V2 and V9.
Optional Samples ^{g, h}																	1		
Optional Genetics sample									Х										Genetics sample can be collected at V2 or at any visit during the Treatment Period. Not applicable for China.
Optional Exploratory Blood Biomarker samples		Х			Х				Х							Х			Must be performed pre-dose at V2 and V9. Not applicable for China. A whole blood sample for transcriptomics (Section 8.6.4.2) is collected at V2 and V16 only.
Collect NP surgery samples – Optional									Х										Wherever possible, the removed tissue from a nasal surgery will be collected and

	Sit 1)a, d						Tı	reatn	nent	Peri	od						Withdraw	/Follow Up	
Procedure	į.							1	Wee	k							EW Visit	Follow-up	N
Flocedule	jing	0	4	8	12	16	20	24	26	28	32	36	40	44	48	52	26 or 52	30/56	Notes
	reeni									Vi	sit (±	7 da	ys)						
	Scr	2a	3a	4 c	5a	6b	7a	8 b	9a	10a	11a	12 ^b	13a	14b	15ª	16a	a, e	b, e	
																			stored. Not applicable for
																			China.
Optional Nasal Biopsy sample																Х			Only in participating countries and sites.

Abbreviations: Ab, antibody; ACQ, asthma control questionnaire; AE, adverse event; ANA, antinuclear antibodies; ANCA, antineutrophil cytoplasmic antibodies; CV, cardiovascular, CRSwNP, chronic rhinosinusitis with nasal polyps; dsDNA, double stranded Deoxyribonucleic acid; ECG, electrocardiogram; eDiary, electronic diary; EW, early withdrawal; INCS, intranasal corticosteroids; NP, nasal polyps; MPO, myeloperoxidase; PGIS, patient global impression of severity; PGIC, patient global impression of change; PI: Principal Investigator; PK, pharmacokinetic; PR3, proteinase 3; SAE, serious adverse event; SF-36, 36 item short form health survey; SNOT-22, 22-item sinonasal outcomes test; SRM, study reference manual; VAS, visual analogue scale; VRS, verbal response scale; WPAI-GH, workers productivity and activity impairment – general health; WOCBP, women of childbearing potential; V, Visit.

- a. In-clinic visit.
- b. Telemedicine visit.
- c. Optional home nursing visit (Week 8; V4 only).
- d. Screening window should be 28 days ± 7 days i.e., maximum of 35 days from Day 1 and minimum of 21 days.
- e. If a participant withdraws from the study, then the EW Visit should be conducted 26 weeks after the last administered dose of study intervention, i.e., at Week 26 if the second dose of study intervention was not received, or at Week 52 if the second dose of study intervention was received. A follow-up visit/call should also be conducted 30 weeks after the last dose of study intervention for AE/SAE assessments, concomitant medication review and pregnancy testing (i.e., at Week 30 or 56).
- f. All questionnaires should be performed before any other assessments on each particular visit.
- g. Informed consent for optional genetics sample or optional exploratory biomarker samples (blood, surgery or nasal biopsy) must be obtained before collecting any samples.
- h. **China only**: Optional samples (genetics, exploratory biomarkers, surgery and nasal biopsy samples) will not be collected from participants in China. Urine dipstick will not be performed in China, all urine sample will instead be sent for central laboratory urinalysis. Investigators should be aware of the time needed for central laboratories to return results, and should perform appropriate local investigations if any urgent result is required.

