8.2. Efficacy Assessments

8.2.1. Endoscopic NP Score

Endoscopic NP score will be assessed at study visits as described in Table 1. This score is graded based on NP size and recorded as the sum of the right and left nostril scores with a range of 0-8; higher scores indicate worse status.

Endoscopic NP score will be performed at the site by trained health care professional (usually ENT surgeon). All image recordings of endoscopies will be sent to an independent reviewer at Clario, the central lab for blinded NP scoring. There is potential for the site score to differ from the central score. In such cases, the output from the central labs is considered final and will be utilized for patient eligibility and for the analysis of this endpoint (for additional details refer to the Clario Video Guideline).

For Visit 2, the nasal endoscopy assessment may be performed up to 7 days prior to the clinic visit but must occur prior to randomization. For all other visits the nasal endoscopy assessment must not exceed the protocol defined windows of ± 7 days from the nominal study visit.

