8.2.2.1. Individual Symptoms Verbal Response Scale (VRS)

All VRS symptom scores will be administered using the eDiary and will be collected daily in the morning from screening to the end of the Treatment Period.

Every day, the participant will be asked to indicate on a VRS, the severity of 4 nasal polyposis symptoms at their worst over the last 24 hours (one VRS for each symptom):

1. nasal obstruction; 2. rhinorrhoea (runny nose); 3. loss of smell; 4. facial pain; 5. mucus in the throat.

A 4-point Likert scale will be used, with appropriate verbal response options of no symptoms, mild symptoms, moderate symptoms, and severe symptoms. Participants will be instructed on how to use the scale prior to use.

Please refer to the SRM for further details on the phrasing of these questions and response options.

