# 4.2. Primary Endpoints Analyses

#### 4.2.1. Definition of endpoints

The co-primary endpoints are:

- a) Change from baseline in total endoscopic NP score at Week 52 (centrally read)
- b) Change from baseline in mean nasal obstruction score (verbal response scale [VRS]) from Week 49 through to Week 52

The total endoscopic NP score is assessed in the clinic at visits 2, 5, 7, 9, 11, 13, 15 and 16, or early withdrawal visit (weeks 0, 12, 20, 26, 32, 40, 48 and 52). The score is then graded by independent reviewers at a central lab who are blinded to treatment. The total score is reported as the sum of the right and left nostril scores and ranges from 0 to 8, with higher scores indicating greater disease severity. Non-missing scores must be available for both sides for the combined score to be calculated; otherwise the score will be set to a value of 9 to indicate a missing or unreadable value.

The nasal obstruction VRS score will be collected daily in the morning via the eDiary. Each day the participant will indicate the severity of their symptoms giving a score ranging from 0 to 3, with the 4 options indicating no symptoms, mild symptoms, moderate symptoms, and severe symptoms. The daily data will be collapsed into thirteen 4-week time periods, with the value for each time period based on the average of the non-missing days covered by that time period as described in Section 6.3.4.2. For each 4-week time period the average will only be derived if there are non-missing values for at least 4 days out of 7 in at least 3 out of 4 weeks, with at least 15 minimum values, otherwise it will be set to missing.

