#### **6.3.4.2.** Daily Diary

Participants are to complete a daily diary assessment each morning. Table 2 below displays which daily diary records are included for each analysis time period. Any daily diary data collected post the 52-week time period will not be included in the Weeks 49-52 analysis of diary data.

Table 2 Daily Diary Assessment Windows

Analysis for A	M Measures		
Beginning Timepoint (Day)	Ending Timepoint (Day)	Analysis Time Period	
-27	1	Baseline	
2	29	Weeks 1 – 4	
30	57	Weeks 5 – 8	
58	85	Weeks 9 – 12	
86	113	Week 13 – 16	
114	141	Weeks 17 – 20	
142	169	Weeks 21 – 24	
170	197	Weeks 25 – 28	
198	225	Weeks 29 – 32	
226	253	Weeks 33 – 36	
254	281	Weeks 37 – 40	
282	309	Weeks 41 – 44	
310	337	Weeks 45 – 48	
338	365	Weeks 49 – 52	

Note: There is no Day 0 in CDISC reporting. Days -27 to -1 are immediately pre-randomization and Day 1 is the day of randomization (Visit 2). For the baseline time period, all values from Day -27 to Day 1 will be included in the baseline average; however, there must be a minimum of 4 non-missing values from Day -6 to Day 1 inclusive in order to derive the baseline, otherwise it will be set to missing.

Note: For each 4-week post-baseline time period the average will only be derived if there are non-missing values for at least 4 days out of 7 in at least 3 out of 4 weeks, with at least 15 minimum values, otherwise it will be set to missing.

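### An in-window early Week 52 visit ends diary entry before the fixed Weeks 49–52 window closes, which makes the co-primary nasal obstruction mean easier to lose

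*Protocol*

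**What the plan says.** **When diary entry ends.** Protocol Table 1 (Section 1.3) states, for the daily VRS and the overall VAS, that the "eDiary will be completed by participants in the morning between Screening Visit (V1) and V16". Its eDiary collection row is marked at V16 and at early withdrawal. Section 8.2.2.1 agrees: the VRS scores "will be collected daily in the morning from screening to the end of the Treatment Period", and V16 is the last Treatment Period visit.

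**When V16 may occur.** Table 1 gives visits a window of ±7 days. The endoscopy note repeats it: assessments "must not exceed the protocol defined windows of ±7 days from the nominal study visit". The same table fixes the day count: "Randomization Day is Day 1".

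**Which days are analysed.** SAP 6.3.4.2, Table 2, gives the final period as "338 365 Weeks 49 – 52", counted from randomization. It covers entries that come too late: "Any daily diary data collected post the 52-week time period will not be included in the Weeks 49-52 analysis of diary data". It has no rule for a V16 that comes early.

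**When the mean is derived.** SAP 4.2.1 requires "non-missing values for at least 4 days out of 7 in at least 3 out of 4 weeks, with at least 15 minimum values"; otherwise the period is set to missing.

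**The concern.** The protocol ties the end of diary entry to a visit that can move. The SAP ties the analysis window to days that cannot. When V16 is late, nothing is lost, because Days 338–365 are already complete. When V16 is early, the end of the window is never collected.

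The endpoint affected is the co-primary nasal obstruction score. The secondary rhinorrhoea and loss-of-smell scores, and the other Weeks 49–52 diary endpoints, share the same diary and window. The completeness rule normally tolerates one poor week in four. A sufficiently early V16 uses up that tolerance before the participant has missed anything. The resulting missing values come partly from a mismatch between two documents, so they are avoidable.

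The responder analyses are the most exposed. SAP 4.4.1 treats a participant with missing data at a time point as a non-responder, and SAP 4.4.2 reports odds ratios and p-values for the nasal obstruction, rhinorrhoea and loss-of-smell VRS responders. A participant who improved and attended within the window could be scored a failure partly because of the visit date.

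**Working it through.** **The plan's own figures first.** Protocol 9.5 gives a difference of 0.70, SD 0.84, 118 evaluable per arm and two-sided 5%.
- Standard error = 0.84 × √(2/118) = 0.1094.
- Power = Φ(0.70/0.1094 − 1.96) = Φ(4.44), above 99.9%. The plan states >99%.
- Smallest significant difference = 1.96 × 0.1094 = 0.21, as stated.

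**Days.** Nominal Week 52 = 1 + 52 × 7 = Day 365. The earliest compliant V16 = 365 − 7 = Day 358. The window holds 365 − 338 + 1 = 28 days, so V16 on Day 358 loses Days 359–365, which is 7 of 28.

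**Weeks.** The SAP does not state how the four weeks are cut. I assume Days 338–344, 345–351, 352–358 and 359–365. With V16 *e* days early, the fourth week has 7 − *e* possible entries. For *e* = 4 to 7 that is at most 3, so the week cannot qualify, and each of the other three must have at least 4 entries. The total must still reach 15.

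**Examples.** Weekly counts 5, 5, 3, 5 give three qualifying weeks and 18 entries: derivable. Lose the last week and 5, 5, 3, 0 is missing. A fully compliant participant seen on Day 358 has 7, 7, 7, 0 (21 entries): derivable.

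**Chance of a missing value.** Assume each day is completed independently with probability *p*, and that the V16 morning entry is made. With n = (7, 7, 7, 7 − *e*),

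P(missing) = 1 − Σ Π C(nⱼ, kⱼ) p^kⱼ (1 − p)^(nⱼ − kⱼ),

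summed over counts with at least three kⱼ ≥ 4 and Σkⱼ ≥ 15. Exact enumeration gives:

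| V16 | Days early | p = 70% | p = 80% | p = 90% |
|---|---|---|---|---|
| Day 365 or later | 0 | 8.22% | 0.64% | <0.01% |
| Day 364 | 1 | 12.12% | 1.26% | 0.02% |
| Day 363 | 2 | 18.59% | 2.81% | 0.07% |
| Day 362 | 3 | 27.36% | 5.92% | 0.28% |
| Day 361 | 4 | 35.36% | 9.89% | 0.82% |
| Day 360 | 5 | 37.88% | 10.38% | 0.82% |
| Day 359 | 6 | 42.52% | 11.72% | 0.85% |
| Day 358 | 7 | 50.00% | 14.97% | 1.00% |

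At 100% completion every cell is 0. If the V16 morning entry is not made on Day 358, 8 days are lost and the 70% figure becomes 62.9%.

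**Trial level.** Assume V16 dates uniform over the 15 days, of which 8 (Days 365–372) lose nothing.
- 70%: (8 × 8.22 + 223.83)/15 = 19.3%, up from 8.2%.
- 80%: (8 × 0.64 + 56.95)/15 = 4.1%, up from 0.6%.
- 90%: 3.86/15 = 0.3%, up from about 0%.

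**Power in an extreme case.** If every V16 fell on Day 358 at 70% completion, about 118 × 0.50 = 59 per arm would have a final-period value. Power = Φ(0.70/(0.84 × √(2/59)) − 1.96) = Φ(2.57) = 99.5%, ignoring what the MMRM recovers from earlier periods.

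**The case against.** Much of the case for leaving the plan alone is sound.

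- **Missing by date alone.** A reader might infer that an early visit makes the endpoint missing. It does not: three full weeks remain even on Day 358. A missing value also needs diary gaps, either a week of fewer than 4 entries among Weeks 49–51 or too few entries in total.
- **The last week discarded.** A reader might infer that every early attender loses the final week. SAP 4.2.1 averages the non-missing days in the period; the weekly count decides only whether the mean is derived. A V16 1–6 days early keeps 6 to 1 days of that week, and only Day 358 loses all of it.
- **The 70% figure.** SAP 6.2.1 sets it as a target across all eCOA instruments, not as a forecast for this diary. Compliance is screened before randomization (Section 5.3, criterion 3) and checked at each visit.
- **Visit dates.** Uniform dates have no basis in the documents. With triangular weights 8 − |d| over 64 (also assumed), the rise is 7.7 points at 70%, 2.3 at 80% and 0.2 at 90%.
- **Inference.** Earlier four-week periods stay in the MMRM under MAR. Blinded visit timing gives no evident reason for loss to differ by arm. After surgery or a disease-modulating medication, a score of 3 is assigned for every later day, so those participants are little affected. Multiple-imputation sensitivity analyses are planned.
- **Unseen instructions.** Table 1 refers to the study reference manual, which may tell sites how to handle the device.

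All of this limits the size of the problem. None of it supplies the missing rule, and the MMRM argument does not help the responder analyses.

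**Conclusion.** The gap is real and modest. Following both documents as written, a compliant early V16 removes 1–7 of the 28 co-primary diary days. From 4 days early, under the assumed week cuts, it turns a three-of-four-weeks requirement into three of three.

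The size depends on diary completion. It matters at 70%, is small at 80% and is close to nil at 90%. The 35–50% figures apply only to participants seen 4–7 days early (4 of 15 days, or 27%, if dates are uniform) and should not be read as trial-level missingness. All figures rest on independent daily completion; the trial-level ones also rest on the assumed visit dates.

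A reader might go further and conclude that the primary result or its power is at risk. The documents do not support that: power stays about 99.5% even in the extreme case above. This is a low-cost improvement that prevents avoidable missing data and some avoidable non-responder classifications. It is not an error that threatens the primary conclusion.

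**What to change.** In Table 1 and Section 8.2.2, state that when V16 falls before Day 365 the participant continues the daily eDiary through Day 365 and returns the device afterwards. Section 10.11.5 already describes return by mail for COVID-19 disruption. All 28 days are then available, and the chance of a missing value at 70% completion returns to 8.2% whatever the V16 date. The cost is a later device return for early attenders.

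Section 10.11.5 also ties the end of diary collection to a Visit 17 exit visit, and Table 1 has no Visit 17. Reconcile the two in the same edit.

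The SAP alternative is to end the final window on the V16 date when that is early. It needs only a sentence but is more debatable: the window becomes participant-specific, and up to 7 days overlap with Weeks 45–48 unless that window moves too. If it is used, it should be fixed before unblinding.
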